### **Specific Aim 2:**

To investigate the association between the gait improvement (i.e. gait speed and walking distance) in walking with C-Brace and baseline neuromuscular, cardiopulmonary characteristics that affects gait performance, cognition and physical function in individuals with hemiparesis or hemiplegia. We also aim to develop an algorithm to characterize the patients who may receive the maximal benefit of using C-Brace for walking. We hypothesize that the improvements observed in walking with C-Brace are related to muscle strength, range of motion, severity of spasticity and the functional status and the degree of relations may be varied. We will then identify the key parameters based on association to develop an algorithm to characterize the patients who may receive the maximal benefit of using C-Brace for walking.

### **Outcome Measures:**

The following assessments will be measured at baseline and follow-up (without wearing C-brace):

- *Folstein Mini Mental State Examination (MMSE):* Mini Mental State Examination provides information about orientation, attention, learning, calculation, delayed recall, and construction. Several studies report acceptable validity of MMSE as a screening instrument and its relationship to functional outcome in stroke population[20].
- *Lower limb muscle strength and range of motion:* Muscle strength will be measured and quantified by using dynamometers on major bilateral lower limb muscles such as hip flexors and extensors, hip abductors and adductors, knee flexors and extensors and ankle dorsiflexors and plantarflexors. Range of motion will be measured on bilateral hip, knee and ankle joints using goniometry.
- *Fugl-Meyer Assessment – Lower Extremity and Balance:* This test evaluates and measures recovery of movement in individual post stroke. Fugl-Meyer has been used in both clinical and research settings and is one of the most widely used quantitative measures of motor impairment [21]. It uses an ordinal scale for scoring of 17 items for

the lower limb component and 7 items on the Balance component of the F-M scale (0: cannot perform; 1: can perform partially; 2: can perform fully).

- *Modified Ashworth Scale (MAS)*: This test measures spasticity in patients with lesions of the Central Nervous System by testing resistance to passive movement about a joint with varying degrees of velocity. Scores range from 0-4, with 6 choices (i.e., 0, 1, 1+, 2, 3, 4), with 0 indicating normal muscle tone, and 4 indicating very high spasticity. We will measure spasticity in lower limbs.
- *Timed Up and Go (TUG) Test*: Assesses mobility, balance, walking ability, and fall risk in older adults. This test has been used in assessing stroke recovery with high reliability and validity [18]. The test measures the time it takes the subject to perform a sit to stand from a chair with arms, walk to a mark on the ground 10 feet away and return to the seated position in the chair with arms.
- *Berg Balance Scale (BBS)*: A 14-item objective measure designed to assess static balance and fall risk in adult populations, with maximum summed score of 56 (higher scores represent better functional outcome). This test has been widely used to measure functional recovery in stroke patients with high reliability [22].
- *10 Meter Walk Test (10MWT)*: Measure of gait speed. Subjects will walk a total of 14 meters at their preferred walking speed and at a fast pace. The test measures the time it takes the subject to complete the middle 10 meters of the walk.
- *Six-minute walk test (6MWT)*: This test assesses distance walked over 6 minutes as a sub-maximal test of aerobic capacity/endurance. It has good responsiveness to detect improvements in capacity to walk in stroke patients [19].
- Orthosis Evaluation Questionnaire: consists of 72 questions as compared to 81 questions in the PEQ to be answered by the patients on a 100-mm visual analogue scale (VAS) with higher values representing better function.

#### Assessment Timeline

Assessment	Screening	Fitting	Baseline	C-Brace Training (3x/wk x 4wks)	Post Training	Home/Community Use	Follow Up
	Visit 1	Visit 2, 3	Visit 4	Visit 5-16	Visit 17	4-6 weeks	Visit 18
10MWT	X		X		X		X
Trial Tool to Operate device and casting	X						
Diagnostic test orthosis and alignment assessment		X					
C-Brace fitting finalized		X					
MMSE			X				X
Muscle Strength	X		X				X
Range of Motion	X		X				X
Fugl-Meyer			X				X
MAS	X		X				X
TUG			X		X		X
BBS			X				X

6MWT			X		X		X
C-Brace Training				X			
sEMG					X		X
Gait Kinematics					X		X
Metabolic					X		X
Orthosis Evaluation Questionnaire							X

## DATA and SAFETY MONITORING

We will use following strategies to prevent some expected events for this study:

1) Loss of confidentiality or privacy

Information obtained for this study will be kept private to the extent allowed by law. However, research information may be shared with the University of Texas Health Science Center at Houston Institutional Review Board (IRB), the research physician investigator, the research staff and others who are responsible for ensuring compliance with laws and regulations related to research.

The study will be performed at UT Health Motor Recovery Laboratory at the TIRR NeuroRecovery Research Center. All data collection records will be locked in the Study Coordinator's office in a locked file cabinet. Energy consumption, sEMG and motion capture files will be saved to the research computer using de-identified data. All computers are password protected and therefore, only authorized persons have the access to the electronic files saved in computers and will adhere to TIRR MEMORIAL HERMANN standards.

2) Loss of saved electronic data after a computer crash

All original data will be maintained on paper data collection forms. De-identified data may be entered into computer for data analysis. A standard procedure of electronic file backup is established and enforced by the PI. All file backups are routinely performed in the local hard drive. However, if there are other unanticipated problems which occur during and after data collection: the original paper version of the data will be maintained in the locked file cabinet.

3) Muscular soreness or fatigue

*Borg Rating of Perceived Exertion Scale* (Borg) will be administrated periodically throughout the intervention sessions. Subject will be provided with rest period as needed, in particular if BORG rating  $\geq 17$ .

4) Loss of balance or fall from testing

All subjects will be able to independently ambulate. The addition of the C-Brace will provide increased stability for the subject when standing and performing transitional movements. Therefore, the use of the C-Brace will reduce the risk of falls for subjects. There is a training period to allow the subject to become familiar with the C-Brace. One research team member will remain next to the subject throughout the training session and during all testing procedures to prevent loss of balance or fall whether sitting or standing. As subjects advance their skills and progress to independent users their fall risk will continue to decrease.

If a fall or significant loss of balance occurs, one staff physician will be notified immediately. All adverse events will be reported per CPHS protocol.

5) Possible skin irritation

Local irritation, bruising, swelling, or temporary discomfort following wearing of the C-Brace may occur. Prior to donning the C-Brace subject's skin will be inspected by a licensed Physical Therapist for baseline, and compared after doffing. Any differences will be recorded and followed up with the study physician accordingly. All adverse events will be reported per CPHS protocol.

## STATISTICS

### Aim 1:

The effects of C-Brace on dependent variables will be analyzed using separate 2-factor (group x condition) analyses of variance (ANOVA) with repeated measures on the walking condition (walking with and without C-Brace). The model will first test for the interaction to determine if 3 groups (mild, moderate and severe) respond similarly across time. In the event of a significant interaction ( $p < .05$ ) we will test for differences between among groups at each point in time (post hoc Tukey).

[figure not shown]

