## STUDY DESIGN

### Subjects

15 individuals with diagnosis of stroke and residual hemiparesis or hemiplegia will be grouped into one of three categories based on their walking speed at baseline. Subjects will receive 4 weeks of gait training utilizing C-Brace, 3 times per week for a total of 12 sessions. We will utilize the 10 Meter Walk Test to assess gait speed for all groups at baseline (week 0). Once training sessions are complete and subject is considered an independent experienced user (week 5) we will assess the neuromuscular and cardiopulmonary responses and gait kinematics during walking with and without C-Brace. Subjects will then continue with use of C-Brace in their daily routine in their home and community environments for 4-6 weeks. Subjects will then return for a follow up visit (week 8-10) and reassessment of neuromuscular and cardiopulmonary responses and gait kinematics during walking with and without C-Brace.

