### **Outcome Measures:**

We will measure the following parameters during gait with and without C-Brace at completion of training sessions and at follow up.

- *Timed Up and Go:* Assesses mobility, balance, walking ability, and fall risk in older adults. The test measures the time it takes the subject to perform a sit to stand from a chair with arms, walk to a mark on the ground 10 feet away and return to the seated position in the chair with arms. This test has been used in assessing stroke recovery with high reliability and validity[18].
- *10 Meter Walk Test (10MWT):* Measure of gait speed. Subjects will walk a total of 14 meters at their preferred walking speed and at a fast pace. The test measures the time it takes the subject to complete the middle 10 meters of the walk.
- *Kinematics and electromyography (EMG):* Bilateral upper and lower extremity kinematics and surface electromyography (sEMG) recordings will be collected during 10MWT. Infrared light emitting diode markers will be attached to bilateral lower extremities. The marker data will be recorded using the NDI Optotrak Certus motion capture system. Marker data will be processed using custom Matlab program to

determine lower extremity joint excursion and joint angular velocities. For EMG, we will place bipolar surface electrodes on the bilateral major leg muscles to record electromyography (1000Hz, Motion Labs 16-Channel EMG System). We will calculate the EMG amplitude and burst duration over the whole gait cycle during the 10MWT.

- *Six-minute walk test (6MWT):* This test assesses distance walked over 6 minutes as a sub-maximal test of aerobic capacity/endurance. It has good responsiveness to detect improvements in capacity to walk in stroke patients [19].
- *Metabolic expenditure during walking:* Oxygen consumption during 6MWT will be determined using a portable metabolic system. Metabolic data will be collected on a breath-by-breath basis during gait assessment. Prior to the testing, the system will be calibrated using room air and reference gas mixture. During the testing, the subject will wear the face mask at all times and will be asked to breathe normally. Subjects will also wear a heart rate monitor. The data will be synchronized with kinematic and electromyography data for further analysis. This task will be performed during walking with and without C-Brace.

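### The Aim 1 ANOVA has no visit factor for the time comparisons it promises, and leaves unused the unbraced baseline that would show which walking condition changed

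*Combined protocol and SAP*

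**What the plan says.** - **Model** (STATISTICS, Aim 1). Separate two-factor ANOVAs, group by condition, "with repeated measures on the walking condition (walking with and without C-Brace"). The interaction is tested first, "to determine if 3 groups (mild, moderate and severe) respond similarly across time". If it is significant at the 5% level, Tukey comparisons of the groups follow at every time point. Visit is not a factor and there is no baseline term.
- **Timing of the contrast** (Specific Aim 1, Outcome Measures). "We will measure the following parameters during gait with and without C-Brace at completion of training sessions and at follow up". These are Visits 17 and 18 in the Assessment Timeline.
- **Exposure by then** (Study Design, Subjects). "Subjects will receive 4 weeks of gait training utilizing C-Brace, 3 times per week for a total of 12 sessions". Visit 18 follows a further 4-6 weeks of home and community use.
- **Unbraced baseline** (Specific Aim 2, Outcome Measures). "The following assessments will be measured at baseline and follow-up (without wearing C-brace"). That list includes TUG, 10MWT and 6MWT, and the Assessment Timeline places all three at Visit 4. The 10MWT is also done at screening (Visit 1). sEMG, gait kinematics and metabolic measures are scheduled at Visits 17 and 18 only.
- **Groups** (Study Design, Subjects; Table 1). Three severity groups of 5, formed on baseline walking speed.

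**The concern.** There are two gaps, and they share a remedy.

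First, the stated model does not match its stated purpose. A group by condition interaction asks whether the brace difference varies with severity. It says nothing about whether that difference changes between Visit 17 and Visit 18. The plan promises a comparison over time and does not say how the two visits enter the analysis.

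Second, the unbraced walk at Visits 17 and 18 is that of someone who has trained in the brace and, by Visit 18, lived with it. If training has carried over, unbraced walking will have improved. If the subject has come to rely on the brace, it will have worsened. The with-minus-without difference moves in both cases, and from that difference alone a reader cannot tell whether the braced or the unbraced walk changed. At stake is the interpretation of the main Aim 1 result: a positive difference could be reported as benefit when braced walking is no better than walking before the study.

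**Working it through.** **1. Design counts.** 3 groups x 5 = 15 subjects and 3 sessions x 4 weeks = 12 sessions, as the plan states. The plan gives no SD, effect size or power, so there is no further figure to reproduce.

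**2. Model against data.** Each Aim 1 outcome yields 15 subjects x 2 conditions x 2 visits = 60 values. A group by condition layout has 15 x 2 = 30 subject-by-condition cells. Each cell therefore holds two values, one per visit, and the plan does not say whether they are averaged, analysed separately or pooled.

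- Group by condition: (3-1)(2-1) = 2 numerator df and (15-3)(2-1) = 12 error df.
- Group by condition by visit: (3-1)(2-1)(2-1) = 2 and (15-3)(2-1)(2-1) = 12. This compares, across groups, each subject's with-minus-without difference at Visit 18 minus the same difference at Visit 17.

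The second test addresses response over time. With complete data, adding visit leaves the group by condition test, averaged over visits, on 2 and 12 df.

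**3. What the contrast contains.** Let B be braced walking, U unbraced walking, 0 Visit 4, and post either later visit. Then

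B_post - U_post = (B_post - U_0) - (U_post - U_0).

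The same-visit difference equals braced change from the unbraced baseline minus change in unbraced walking. All speeds below are assumed. With B_post - U_0 = 0.10 m/s:

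| Unbraced change U_post - U_0 | Same-visit difference |
|---|---|
| -0.05 | 0.10 + 0.05 = 0.15 |
| 0 | 0.10 |
| +0.05 | 0.10 - 0.05 = 0.05 |
| +0.10 | 0.10 - 0.10 = 0.00 |

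Two different histories can also give one result. Braced +0.04 with unbraced unchanged gives 0.04 - 0 = 0.04 m/s. Braced unchanged with unbraced 0.04 worse gives 0 - (-0.04) = 0.04 m/s. Only U_0 separates them. It is scheduled for TUG, 10MWT and 6MWT, and does not exist for sEMG, kinematics or metabolic cost.

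**4. A hazard in using U_0 by group.** If groups are cut on the same 10MWT that serves as U_0, measurement error produces an apparent change of (1 - reliability) x (overall mean - group mean). Assume normal speeds with mean 0.60 and true SD 0.30 m/s, and the plan's 0.4 m/s cut for severe.

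- Reliability 0.85: observed SD 0.30/√0.85 = 0.325, severe group mean 0.201, spurious change 0.15 x 0.399 = +0.06 m/s.
- Reliability 0.95: observed SD 0.30/√0.95 = 0.308, severe group mean 0.215, spurious change 0.05 x 0.385 = +0.02 m/s.

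The mild group (above 0.8 m/s) mirrors this at -0.06 and -0.02 m/s. The artefact runs in the direction Aim 1 hypothesises. When groups are formed on the separate screening 10MWT, simulation under the same assumptions, with independent errors at the two visits, gives about zero in every group.

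**The case against.** The strongest defence is that the plan measures what Aim 1 asks. The aim is to compare walking with and without the device, and testing is deliberately placed after subjects have become experienced users. A same-visit comparison removes training, practice and recovery shared by both conditions, and is largely protected from regression to the mean. All of this stands.

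A reader might therefore go too far in two ways.

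- **That the Aim 1 contrast is biased by carry-over.** It would be so only if the target were gain over pre-training walking, and the natural reading of Aim 1 is the same-visit difference. Suppose severe subjects gain 0.12 braced and 0.08 unbraced, and mild subjects 0.06 and 0.02. Both differences are 0.04 m/s, and a zero interaction is the correct answer about the device. Likewise, suppose braced gains over baseline are equal and unbraced carry-over differs by 0.05-0.15 m/s between the extreme groups, evenly spaced. The chance of a significant interaction is then 0.06 to 0.97 for assumed SDs of the differences of 0.20 down to 0.05. That is not an inflated false-positive rate, because the device effect in trained users really does differ between groups.
- **That baseline data are ignored throughout.** Baseline speed forms the groups and may enter Aim 2 through changes in speed and distance, whose reference point is undefined. The unused values are the three walking tests, and only within Aim 1.

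It could also be said that time is a slip for condition, or that the separate ANOVAs are meant to be run at each visit. Either is possible. Under the first, handling of the two visits remains unstated. Under the second, two separate analyses still do not test whether the response changes between visits.

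**Conclusion.** The concern holds as a gap in specification and interpretation, and the Statistics section should be changed. It is not an error in the contrast. That visit is missing from the stated model, and that Visit 4 values are unused in Aim 1, follows directly from the text. That the same-visit difference cannot show which condition moved follows from the identity and needs no assumption. The difference shifts one for one with any change in unbraced walking, but the documents give no size, direction or group pattern for that change, so its practical effect cannot be fixed. Every speed, SD and reliability used above is an assumption.

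**What to change.** 1. State that the Aim 1 effect is the with-minus-without difference at the same visit, in trained users.
2. Replace the two-factor model with a group by condition by visit repeated-measures or mixed model, with condition and visit (17, 18) within subject. Reword the time statements to match its terms.
3. For TUG, 10MWT and 6MWT, also report by group, with confidence intervals and labelled supportive: (a) unbraced change from Visit 4 to Visits 17 and 18; (b) braced walking at Visits 17 and 18 minus unbraced Visit 4. Label (b) as brace plus training, practice and recovery, since there is no control arm.
4. For these by-group changes, form the groups from the screening 10MWT, or state the caution on regression to the mean.
5. For sEMG, kinematics and metabolic outcomes, state that carry-over cannot be assessed.

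The cost is revised wording and slightly more analysis. All the measurements are already scheduled. With 5 subjects per group the added quantities are descriptive, not confirmatory.

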## OBJECTIVES

Specific Aim 1: To quantify and compare the neuromuscular, cardiopulmonary responses and gait kinematics during walking with and without C-brace in individuals with hemiparesis or hemiplegia. We plan to recruit patients with hemiparesis or hemiplegia following stroke and include a wide range of gait impairments. It is expected that subjects will demonstrate various degree of difference in energy expenditures, neuromuscular responses, functional status and gait characteristics between walking with and without C-brace, depending on their current walking ability. We hypothesize that the changes in cardiopulmonary responses, neuromuscular responses of major lower muscle groups and gait characteristics would be greater in persons with lower functional status and severe gait impairment.

Specific Aim 2: To investigate the association between gait improvement (i.e. gait kinematics, speed and walking distance) in walking with C-Brace and baseline neuromuscular, cardiopulmonary characteristics that affect gait performance, cognition and physical function in individuals with hemiparesis or hemiplegia. We also aim to develop an algorithm to characterize and subgroup the patients who receive gait training with C-Brace. We hypothesize that the improvements observed in walking with C-Brace are related to muscle strength, range of motion, severity of spasticity and the functional status, and the degree of relations may be varied. We will then identify the key parameters and measures based on association to develop an algorithm to characterize the patients who may receive the maximal benefit of using C-Brace for walking.

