## **Study Population**

15 individuals with hemiparesis or hemiplegia after stroke in the Houston metropolitan area. Inclusion and exclusion criteria are listed in Table 1. Participants will be screened and evaluated by study investigators and certified physical therapists. We plan to recruit individuals with a wide range of walking abilities. The walking ability will be determined by gait speed from 10 meter walk test: severe gait impairment (gait velocity <0.4 m/s, moderate gait impairment (gait speed 0.4-0.8 m/s) and mild impairment (gait speed >0.8 m/s)[17].

Table 1:

	Inclusion Criteria	Exclusion Criteria
15 subjects (5 subjects in each group) • Mild • Moderate • Severe	

• Age 18 - 65 years

• Diagnosis of hemiparesis or hemiplegia following stroke

• Presence of abnormal walking pattern

• Poor knee control during stance phase

• Cognitive ability to (or care provider) manage daily charging of battery

• Cognitive ability to follow commands

• Hip flexor muscle strength grade 3 or greater or the ability to perform reciprocal gait using compensatory patterns

• Able to operate C-brace

	

• Weight > 275 lbs. (Includes body weight and weight of heaviest object carried)

• Less than 2° of ankle motion

• Severe spasticity of the quadriceps (MAS >3) and/or uncontrolled spasticity of the quadriceps

• Severe spasticity of other lower limb muscles (MAS >3)

• Fixed genuvalgum exceeding 10° beyond anatomic neutral valgum

• Any fixed genuvarum exceeding anatomic neutral varum.

• Hip or knee flexion contractures greater than 10°

• Presence of COPD

• Chronic heart failure – NYHA stages 3 and 4

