### **Specific Aim 1:**

To quantify and compare the neuromuscular, cardiopulmonary responses and gait kinematics during walking with and without C-brace in individuals with hemiparesis or hemiplegia. We plan to recruit patients with hemiparesis or hemiplegia following stroke who present with gait impairments. It is expected that subjects will demonstrate varying degrees of energy expenditures, neuromuscular responses, functional status and gait characteristics between walking with and without C-brace, depending on their current walking ability. We hypothesize that the changes in cardiopulmonary responses, neuromuscular responses of major lower muscle groups and gait characteristics will be greater in persons with lower functional status and more severe gait impairments.

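### Aim 1 predicts an ordered gradient but tests it only with an unordered 2-df interaction; a 1-df trend contrast on the same groups fits the hypothesis better

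*Combined protocol and SAP*

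**What the plan says.** The hypothesis is ordered. OBJECTIVES, Specific Aim 1, expects that changes in cardiopulmonary, neuromuscular and "gait characteristics would be greater in persons with lower functional status and severe gait impairment". The restatement under STUDY PROCEDURES, Specific Aim 1, says the same.

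The groups come from one measured quantity, 10MWT speed. Study Population defines them as "severe gait impairment (gait velocity <0.4 m/s, moderate gait impairment (gait speed 0.4-0.8 m/s) and mild impairment (gait speed >0.8 m/s" and Table 1 plans "15 subjects (5 subjects in each group". The speed itself is on record for every subject: "We will utilize the 10 Meter Walk Test to assess gait speed for all groups at baseline (week 0". The Assessment Timeline places the baseline 10MWT at Visit 4.

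STATISTICS, Aim 1, plans "separate 2-factor (group x condition) analyses of variance (ANOVA) with repeated measures on the walking condition". The interaction is tested first, to "determine if 3 groups (mild, moderate and severe) respond similarly across time". If it is significant at .05, Tukey comparisons between groups follow at each point in time. The documents plan no ordered contrast and no model with continuous baseline speed. The Aim 2 regression does not list baseline speed among its predictors. There is no power or sample-size calculation.

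**The concern.** The hypothesis says which way the groups should differ, and the test does not use that. A 2-df interaction gives a pattern in which the moderate group changes most the same weight as the predicted gradient from mild to severe. The Tukey step does not repair this: it is also unordered, it compares group levels at a time point rather than group changes, and it runs only after a significant interaction.

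A smaller loss comes from cutting speed at 0.4 and 0.8 m/s: subjects at 0.41 and 0.79 m/s count as the same, while subjects at 0.39 and 0.41 m/s count as different.

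With 15 subjects, a real gradient could easily give a non-significant interaction. In the plan's wording, that result invites the conclusion that the groups respond similarly.

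**Working it through.** **Inputs from the documents:** 3 groups of 5, cut points 0.4 and 0.8 m/s, 2 walking conditions, alpha .05. There is no stated power to reproduce.

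**Assumed, because the documents give nothing:** speeds uniform over 0.1-0.4, 0.4-0.8 and 0.8-1.2 m/s within the groups; residual SD of the difference set to 1; severe-to-mild gap of 0.5 to 2.0 SD.

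**Step 1: reduce the model.** With two conditions, the interaction F equals a one-way ANOVA F on each subject's with-minus-without difference (checked numerically: both 0.3442). Its df are (3-1)(2-1) = 2 and 15-3 = 12. The linear trend contrast, weights -1, 0, 1, has 1 and 12 df. Regression on speed has 1 and 13 df.

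**Step 2: change linear in speed, gap 1.5.**
- Group mean speeds are 0.25, 0.60 and 1.00 m/s, so the slope is 1.5/0.75 = 2.0 SD per m/s.
- Group mean changes relative to speed zero are -0.5, -1.2 and -2.0, with mean -1.233. Squared deviations sum to 0.538 + 0.001 + 0.588 = 1.127.
- Within-group variance is 1 + 2.0² x (0.3² + 0.4² + 0.4²)/36 = 1.046.
- Noncentrality of the 2-df test: 5 x 1.127/1.046 = 5.39. Power is 43%.
- Noncentrality of the trend contrast: 1.5² x (5/2)/1.046 = 5.38. Power is 57%.

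The contrast carries almost all of the signal on one df, so the second df of the planned test buys almost nothing for this pattern.

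**Step 3: power by simulation, linear case, two-sided .05.**

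| Gap (SD) | Planned 2-df | Trend contrast | Continuous speed |
|---|---|---|---|
| 1.0 | 22% | 31% | 35% |
| 1.5 | 43% | 57% | 64% |
| 2.0 | 67% | 80% | 86% |

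Repeat runs agree within about two points, and type I error is 5% for all three. At 0.5 SD both ordered tests gain only 2 to 3 points.

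At 1.5 SD the trend contrast gains 57 - 43 = 14 points of the 64 - 43 = 21 available, or two thirds. At 1.0 SD it is 9 of 13 and at 2.0 SD 13 of 19. Most of the loss is therefore from ignoring order; the rest is from cutting speed.

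**Step 4: the same comparison by correlation.** If speed and change correlate at 0.5, power is 36%, 48% and 54% (planned, trend, continuous). At 0.6 it is 55%, 69% and 76%. For 80% power the three tests need correlations of about 0.71, 0.66 and 0.62. With one dropout per group and correlation 0.6, power is 42%, 57% and 64%.

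**Step 5: change steps at a cut point.** If only the severe group differs, by 1.5 SD, noncentrality is 5 x 1.5² x 2/3 = 7.5 for the planned test and 1.5² x 5/2 = 5.63 for the trend contrast. Power is 57% and 59%. Continuous speed gives 46%, or about 51% if the step is at the mild group instead. At 2.0 SD with only the severe group different, the planned test has 83% and continuous speed 66%.

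**Step 6: moderate group changes most.** With the same explained variance as a correlation of 0.6, the planned test has 63% power and both 1-df tests 5% or less.

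**The case against.** The planned test is valid, holds its 5% error rate and matches the stratified recruitment. The hypothesis says greater, not linear, and would also be met by a threshold. The cut points come from a cited classification of walking handicap. Under a threshold, regression on speed loses 6 to 11 points to the planned test at 1.5 SD. The gain is also small when the effect is small. Even after the change, 80% power needs a correlation of about 0.62 with 15 subjects. Finally, the hypothesis also names functional status, which speed alone does not capture.

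All of this stands, and it limits the point without removing it. The threshold argument counts against making continuous speed the lead test. It does not count against the trend contrast, which gains under a linear gradient and loses essentially nothing under a step. The only shape for which the planned test is clearly better is non-monotone, and Aim 1 does not posit one.

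**Conclusion.** The point holds as a mismatch between hypothesis and test, and as a cheap gain in efficiency. The planned analysis is not an error. If change is roughly linear in speed and the gap is 1.0 to 2.0 SD, the trend contrast adds about 9 to 14 points of power and continuous speed about 13 to 21. These sizes depend on the assumed gaps and speed distribution.

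A reader might infer three stronger things that the documents do not support:
- **That the plan gives up this power under any response shape, at no cost to recover.** The data are already collected, but the gain depends on shape and size; it nearly vanishes at 0.5 SD, and the advantage of continuous speed reverses under a step.
- **That categorising speed is the main fault.** About two thirds of the loss is recovered with the categories left as they are.
- **That the interaction is the main Aim 1 test.** The documents name no primary test or outcome, and Aim 1 also sets out to compare the two walking conditions overall.

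**What to change.** In STATISTICS, Aim 1:
- Name a 1-df linear trend contrast across severe, moderate and mild, on each subject's with-minus-without difference, two-sided at .05, as the test of the gradient hypothesis. It should not depend on a significant interaction.
- Add regression of that difference on continuous Visit 4 preferred-pace 10MWT speed as the supporting analysis.
- Keep the 3-group interaction as a check on shape, and the strata for recruitment and description.
- State that the gradient result is exploratory, and report the estimate with its confidence interval. A non-significant result is not to be read as evidence that the groups respond similarly.

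The cost is analysis wording: no added visit, assessment or subject. The downside is that the ordered tests have little power for a non-monotone pattern; the retained interaction covers that case.
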